Currently, many alternatives to autograft harvest are being evaluated for foot and ankle arthrodesis. Given the known complications of autograft harvest (incision pain, nerve injury, infection, 1), alternatives which possess osteogenic, osteoconductive, and osteoinductive properties are an attractive option when supplementing complex hindfoot arthrodesis procedures. A recent publication demonstrated a superior fusion rate for purified recombinant human platelet-derived growth factor BB homodimer (rhPDGF-BB) when compared to autograft (5). However, arthrodesis rates, as confirmed on CT scan, were only 84% and 65% respectively.

ViviGen (Depuy Synthes) is a cellular bone matrix, which includes viable osteoblasts within a corticocancellous and demineralized bone carrier, represents a unique alternative to autograft or existing products which utilize mesenchymal stem cells. ViviGen Cellular Bone Matrix is a Human Cells, Tissues, and Cellular and Tissue-based Product (HCT/P) as defined by the U.S.

Version Date: 08/19/2021 Page Number: 1 of 10

Food and Drug Administration in 21 CFR 1271.3(d). ViviGen Cellular Bone Matrix is processed from donated human tissue, resulting from the generous gift of an individual or his/her family. This product is classified as a **biologic** by the FDA. Given our encouraging early data using Vivigen for complex and revision arthrodesis procedures in the foot and ankle, our Foot and Ankle Clinical research group at the University of Virginia wishes to conduct a prospective study to evaluate 1-Year implant survivorship in subjects who receive the implant when used for primary ankle or hindfoot arthrodesis procedures as part of their clinical care.

Our study would prospectively follow primary ankle or hindfoot arthrodesis procedures. Ankle arthrodesis, tibiotalocalcaneal arthrodesis, subtalar and triple arthrodesis procedures would be included in this cohort, and CT scan would be utilized to demonstrate successful arthrodesis (defined by >50% fusion). Patient outcome measures including Foot and Ankle Activity Measures, AOFAS hindfoot score, and VAS pain scores would be recorded pre-operatively and for 1 year post operatively.

The purpose of this study is to examine 1-year outcomes. ViviGen Cellular Bone Matrix is being given as part of clinical care. The only research procedures are questionnaires and blood draw for Vitamin D.

Objectives/Hypothesis

INSTRUCTIONS:

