If this study involves biomedical research clearly state the objectives and hypotheses and clearly define the primary and any secondary outcome measures. If this study involves qualitative research clearly state your research hypothesis or question.

This section should not include information already included in other sections such as background information or information from the procedures section.

Answer/Response: To evaluate 1-Year implant survivorship in subjects who receive the implant when used for primary ankle or hindfoot arthrodesis procedures.

Study Design: Biomedical

1. Will controls be used?

Answer/Response: No.

► IF YES, explain the kind of controls to be used.

Answer/Response:

2. What is the study design?

Example: case series, case control study, cohort study, randomized control study, single-blind, double-blind, met-analysis, systematic reviews, other. You may also view the IRB-HSR Learning Shot on this topic to help you answer this question. (http://www.virginia.edu/vpr/irb/learningshots/Writing protocol June09/player.html

Answer/Response: This is a post-market, prospective, non-randomized, PI initiated, open-label clinical evaluation of the implant for use in primary ankle or hindfoot

Version Date: 08/19/2021 Page Number: 2 of 10

arthrodesis. Data will be collected at specific time points and entered into case report forms (CRFs) based on the information contained in the patient medical records.

3. Does the study involve a placebo?

Answer/Response: No.

▶ IF YES, provide a justification for the use of a placebo

Answer/Response:

Human Participants

 Ages:
 18-80

 Sex:
 All

 Race:
 All

Subjects- see below

INSTRUCTIONS: For question 1-4 below insert an exact #. Ranges or OPEN is not allowed. This # should be the maximum # you expect to need to enroll (i.e. sign consent) If you are only collecting specimens the number of participants should equate to the # of specimens you need. If you are collecting only data from a chart review the number should designate the number of subjects whose medical records you plan to review. Age/ Sex/Race criteria should designate the demographics of participants from whom you will obtain the specimen/data.

1. Provide target # of subjects (at all sites) needed to complete protocol.

INSTRUCTIONS: If this is NOT a database protocol, this number should be the same as the number of subjects needed to obtain statistically significant results.

Answer/Response: 15

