- --Recap of study objectives and endpoint definitions. An assessment of how study objectives will be assessed by identifying & defining which endpoints will be used to assess each component of the study objectives.
- --The study design should include contingencies for early stopping, interim analyses, stratification factors (If applicable), and any characteristics to be incorporated in analyses.
- --The power/precision of the study to address the major study endpoint(s), the assumptions involved in the determination of power/precision.
- --If statistical hypothesis testing is included then specify the null and alternative hypotheses, the test statistic, and the type I and II error rates
- --If precision of an estimate, then provide a definition for precision
- --If other, then specify

Answer/Response: We will compare primary outcome measures as a binary outcome using chisquare or Fisher exact analyses using existing failure rates as a historical control. We will use standard parametric statistical analyses to determine change from pre-post surgery and referencing historical control data obtained from the literature. Multivariate statistical modelling will be considered for potential sources of confound if appropriate.

3. Provide a justification for the sample size used in this protocol.

Include the anticipated accrual rate, the accrual goal for the study, including accrual goals by strata if appropriate, adjustments for drop-outs etc. and study duration.

Answer/Response: ViviGen is already an FDA approved biologic, therefore a large sample size is not needed.

4. What is your plan for primary variable analysis?

Include a sketch of the analysis to assess primary study objectives.

Answer/Response: Radiographic evidence of successful arthrodesis confirmed on CT (defined by >50% fusion)

5. What is your plan for secondary variable analysis?

Include the following:

- -- A sketch of the analysis to assess secondary study objectives.
- --For phase III studies, the power/precision of the study to address the secondary objective(s).

Answer/Response:

- Clinical & Radiographic evidence of failure (obvious non-union or hardware failure)
- Patient reported outcomes scores
- Vitamin D levels

6. Have you been working with a statistician in designing this protocol?

Answer/Response: No.

IF YES, what is their name?

Answer/Response:

Version Date: 08/19/2021 Page Number: 6 of 10

7. Will data from multiple sites be combined during analysis?

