If you decide to be in this study, you will read and sign this consent form before any study related procedures take place. You will meet with the study doctor to determine if you are eligible and it is safe for you to participate in the study. This will include the following:

The following procedures will be done as **part of your clinical care** and recorded for research purposes in preparation for your arthrodesis surgery.

- Reviewing your medical history, including your smoking history and current alcohol use.
- Physical exam as well as your weight and height
- Review your current medications.
- If you are a female and able to have children, your physician will ask if you are pregnant and may perform a urine or serum pregnancy test to confirm that you are not pregnant.
- If you are not already currently taking Vitamin D supplements, it will be prescribed to you by your surgeon as part of your standard of care before surgery

The following procedures/assessment will be done solely for research purposes:

- Complete study questionnaires that will ask you about your level of pain, your daily activities, physical function, and quality of life. The questionnaires will take about 20 minutes to complete.
- Laboratory testing including collection of blood samples (1 ½ teaspoons)
 - o Your blood will be analyzed to assess your Vitamin D levels

VISIT 2: SURGERY (as part of your clinical care) (will last about 2 ½ hours):

The following procedures will be done as **part of your clinical care** in preparation for your arthrodesis surgery. The results will also be recorded for research purposes:

- Recording of admission and surgical information from your medical chart
- Primary ankle or hindfoot arthrodesis using the ViviGen graft
- Surgical images of the hindfoot/ankle (intra-operative fluoroscopy and post-operative x-ray)

FOLLOW-UP (each visit will add about 45 minutes to your visit): VISIT 3 –2 Weeks Post Surgery

The following procedures will be done as **part of your clinical care.** The results will be recorded for research purposes:

- Wound Check
- Physical assessment of the hindfoot/ankle, including vital signs

VISIT 4 - 6 Weeks Post Surgery

Version Date: 08/19/2021 Page Number: 8 of 10

The following procedure will be done as **part of your clinical care.** The results will be recorded for research purposes:

- Physical assessment of the hindfoot/ankle, including vital signs
- X-rays of the hindfoot/ankle

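### The only stated objective, 1-year implant survivorship, is undefined and is not the primary variable, and the CT fusion rule does not say how a subject who fused after revision counts

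*Combined protocol and SAP*

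**What the plan says.** Objectives/Hypothesis gives a single aim: "To evaluate 1-Year implant survivorship in subjects who receive the implant when used for primary ankle or hindfoot arthrodesis procedures". Background says the same, describing a "prospective study to evaluate 1-Year implant survivorship in subjects who receive the implant", and adds that the study's purpose is to look at outcomes at 1 year. Neither place says what survival or failure of the implant means.

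Under Statistical Considerations:

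- Question 4 (primary variable) answers: "Radiographic evidence of successful arthrodesis confirmed on CT (defined by >50% fusion". No visit is named.
- Question 5 (secondary variables) lists "Clinical & Radiographic evidence of failure (obvious non-union or hardware failure", patient-reported scores and Vitamin D levels.
- Question 2 treats the primary outcome as binary and compares it by chi-square or Fisher test "using existing failure rates as a historical control". The form's own guidance for that question asks for "identifying & defining which endpoints will be used to assess each component of the study objectives".

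In Study Procedures, Visit 2 covers the index operation ("Primary ankle or hindfoot arthrodesis using the ViviGen graft") and "Recording of admission and surgical information from your medical chart". CT stands in the research list for Visits 5, 6 and 7 (3, 6 and 12 months) without a visit restriction, whereas the blood draw in the same list is limited to 6 months. Study Design, question 2, says the case report forms (CRFs) are filled from the medical records. Revision or a second operation is mentioned only in Background, with no counting rule.

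**The concern.** A study should be able to report the quantity that its objective names. Here the objective is survival of an implant to 1 year, while the analysis is of bone bridging on CT. The two can differ in either direction. A graft can stay in place without 50% fusion, and a joint can be fused at 12 months because the first graft failed and was replaced.

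The second case matters for the primary result. If nothing says how a revised subject counts, the decision falls to whoever analyses the data, after the outcomes are known. The study is open-label, has no control group and compares its rate with historical failure rates, so no concurrent arm is subject to the same choice. With 15 subjects, one reclassification is visible in the headline rate.

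**Working it through.** **1. The plan's own figure.** The target is 15 subjects, with 10% screen failure, dropout or withdrawal expected: 15 / 0.9 = 16.7, so 17. The stated enrolment is 18, which agrees within one subject. The target of 15 has no stated power or precision, so it cannot be reproduced.

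**2. Objective against listed variables.**

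| Listed variable | Measures survivorship? |
|---|---|
| CT fusion above 50% (primary) | No. It measures the state of the joint on a scan, whatever operations came before. |
| Failure item (secondary) | In part. It covers evident non-union and hardware failure, but has no time point, does not name revision, re-grafting or removal, and is not linked to the objective. |
| Patient-reported scores, Vitamin D | No. |

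Followed as written, the plan yields a fusion rate and a count of failures of one kind, but no 1-year survivorship figure.

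**3. One revised subject under the rules.** Take a subject unfused at 6 months, then revised, and more than 50% fused on the 12-month CT.

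- Literal rule, 12-month CT: success.
- Rule applied to the index operation described at Visit 2: failure.
- 3- or 6-month CT as the deciding scan: failure.
- Secondary failure item: the non-union would normally be recorded as a failure.

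The plan does not choose between these.

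**4. Size per subject.** 1/15 = 6.7 points; 1/18 = 5.6 points. For example, 13/15 = 86.7% (exact 95% CI 59.5 to 98.3) becomes 14/15 = 93.3% (68.1 to 99.8).

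**5. Could a conclusion change? Illustration only.** The documents name no comparator, significance level or revision rate. Assume 15 subjects, an exact two-sided one-sample binomial test at 5%, and the 12-month CT as decider.

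- Comparator 65% (the autograft CT rate in Background): 13/15 gives p = 0.104 and 14/15 gives p = 0.027. One subject can cross the line.
- Comparator 60% (the complement of 40% ankle non-union in Background): 12/15 gives p = 0.186 and 13/15 gives p = 0.037.
- Comparators 84% and 90% (the growth-factor CT rate, and the complement of 10% non-union): even 15/15 gives p = 0.151 and 0.390. A switch to a favourable conclusion is impossible.

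For the 65% comparator, let F ~ Bin(15, π) be the number fused without revision, and R ~ Bin(15 − F, s) the number revised and then fused by month 12. The chance of a switch is P(F ≤ 13 and F + R ≥ 14).

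| Assumed share s | π = 84% | π = 65% |
|---|---|---|
| 2% | 1% | 0.2% |
| 5% | 3% | 0.6% |
| 10% | 6% | 1% |
| 25% | 17% | 5% |

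No value of s has a source in the documents.

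**6. Losses.** If 2 of the 18 enrolled were lost before 12 months (10% of 18 is 1.8), they would be 2/18 = 11.1% of the denominator, more than the one-subject shift in step 4. For example, 14 fused is 14/16 = 87.5% of those assessed and 14/18 = 77.8% with losses counted as failures. The plan has no rule for this either.

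**The case against.** The strongest reply has five parts.

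- **The failure item is a proxy for survivorship.** This stands in part. A reader might infer that no listed variable bears on survivorship at all, and the documents do not support that. The proxy is nevertheless secondary and undated, and it is silent on revision and removal.
- **Month 12 is obvious.** The objective is a 1-year one and Background speaks of 1-year outcomes. This largely stands: on its own, the unnamed scan is a missing detail. But month 12 is also the reading under which a revised subject meets the success rule.
- **Reoperations may well be captured.** This stands. A reader might infer from the visit lists that they are not recorded. Those lists are written for participants and are not a list of CRF fields; the CRFs draw on the chart and are not in the documents. Capture is unknown, not shown to be absent.
- **The bias is not one-way.** This stands. Counting revised subjects as fused raises the rate relative to a rule that counts them as failures. Relative to the literal rule, judging the index operation or using an earlier scan can lower it. It would be too strong to say that the open choice can only favour the product.
- **The objective could simply be reworded.** The form itself says that an objective which cannot be analysed should go. Restating the aim as 12-month CT fusion would close the mismatch and is a legitimate choice, but the rule for revised subjects would still be needed.

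**Conclusion.** The point holds in a limited form. The only objective is undefined, is not the primary variable and is not answered by the listed analyses. Separately, the primary rule, read literally at month 12, counts a subject who fused after revision as a success. The plan does not state that this is intended; it is silent.

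The size is 6.7 points per such subject with 15 subjects, or 5.6 with 18. A reader might infer that the study's conclusion is likely to reverse. The documents do not support that: they give no revision rate and name no comparator. A subject would also have to be diagnosed, reoperated and more than 50% fused within 12 months of the index surgery. Under the assumptions in the working, the chance of a switch runs from 0.2% to 17% against a 65% comparator and is nil against 84% or 90%. The case for change rests on the unanswered objective and the unstated rule, both of which are cheap to settle in advance.

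**What to change.** 1. In Objectives and question 4, define 1-year survivorship as no re-grafting, no revision arthrodesis, and no removal or replacement of graft or fixation because of failure or infection, through 12 months. Elective hardware removal after CT has shown fusion does not count as an event. Confirm that the CRF records the date, procedure and reason for each reoperation from the chart. Report the proportion with an exact (Clopper-Pearson) 95% CI.
2. In question 4, name the 12-month CT as the primary assessment. Count as not fused any subject who, before it, had re-grafting, revision arthrodesis, or re-fixation for non-union or hardware failure. Re-fixation needs to be included, because otherwise a rescued failure could still pass as a success.
3. State how many subjects were lost before 12 months. Report the result both among those assessed and with losses counted as failures.

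The cost is a few sentences and a few chart-review fields, with no added visit, scan or subject. The downside is a possibly lower reported success rate.
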